## 12.5 Visits

The study visits and procedures will be undertaken by one of the clinical trials team. The procedures to be included in each visit are documented in the schedule of attendances (see Appendix A). Each visit is assigned a time-point and a window period, within which the visit will be conducted. If a participant cannot attend a visit, where possible, this will be re-arranged to an in-person visit within the time window. The final visit will be conducted via a digital questionnaire administered by uMed. If the questionnaire has not been completed following additional prompts by the uMed nursing delegate, then the local study team will be contacted to attempt reach out to the participant's family.

#### 12.5.1 Vaccination

Volunteers will be considered enrolled to the trial at the point of randomisation. All vaccines will be administered nasally according to specific SOPs (Equivalent to NHS guidelines for administration of LAIV).

#### 12.5.2 Diary reports

Participants' parents/legal guardians will receive a digital diary request at 7 and 14 days after each inperson study visit during the trial, issued via uMed. This will ask them whether their child has attended a healthcare provider since their last visit or diary entry. If they answer yes, they will be directed to further questions regarding the location and nature of this contact with a healthcare provider.

Participants will not be provided with a 24-hour telephone number to contact the study team for medical advice, as this would significantly impact the primary outcome measure which is dependent on the participant's family conducting their normal healthcare seeking behaviour. Participants will be advised to seek their normal routes of healthcare advice via NHS provision of they have any medical concerns regarding their child, whether or not they are considered related to the study. This information will be captured via the digital diary.

Participants will be provided with a 24h telephone number and email address to report hospital admissions to the study.

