## 9 Objectives and Outcome Measures

Objectives	Outcome Measures	Timepoint(s)			
Primary					
To determine the safety and reactogenicity of LAIV in children	Episode of respiratory wheeze requiring medical attention diagnosed by a health practitioner	Day 0 to 28 following vaccination			
	Key secondary				
To assess safety of LAIV	Serious adverse events	Throughout the study			
	All medically attended adverse events	Throughout the study			

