## 9.1 Outcome ascertainment

Outcomes will be collected from routine GP medical records by the digital CRO, uMed. For medically attended wheeze, specific codes referring to a diagnosis of "Viral induced wheeze" and "Asthma" will be used, alongside findings of "Wheeze", and any new prescription for either Salbutamol or Ipratropium Bromide:

- 276191000000107 | Viral wheeze (disorder)
- 195967001 | Asthma (disorder)
- 56018004 | Wheezing (finding)
- 24612001 | Wheeze rhonchi (finding)
- 372897005 | Salbutamol (substance)
- 372518007 | Ipratropium (substance)

Whilst using codes of a finding of "wheeze" are most specific to the primary outcome, these codes are rarely used in practice and yield insufficient events. GP EPR data from a 3 month period indicates that, "Viral induced wheeze", and "Asthma" are the codes most commonly associated with wheezing. This

yields a population incidence of roughly 2% during a three-month period, in line with the power calculations for the study.

The primary outcome includes all events coded with a finding of "wheeze" together with the addition codes asthma/viral wheeze/salbutamol/ipratropium.

Additional medical attendances at locations other than the child's primary GP practice (e.g., hospital or other GP locations) will be determined using electronic diaries and solicited at follow up visits.

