## 14.7 Reporting Procedures for Serious Adverse Events

Study sites can be alerted to SAEs via three mechanisms:

• Direct solicitation at follow-up visits.

- Participant reports hospital admission in eDiary (uMed will then notify trial site).
- Participant directly reports SAE to uMed via central telephone number or email on study card (uMed will then notify trial site).

Once the site had been notified of an SAE, the site investigator is required to complete the SAE CRF to notify the Chief investigator or delegate. This may require the investigator to contact the participant's parent/legal guardian to gather information regarding the nature of the SAE. If report of the SAE has come via uMed, they will also notify the CI/delegate of its occurrence so they are aware of a pending report.

In order to comply with current regulations on SAE reporting to regulatory authorities, the event will be documented accurately and notification deadlines respected. SAEs will be reported promptly once the local Investigator/study team becomes aware of their occurrence. Copies of all reports will be forwarded for review to the Chief Investigator (as the Sponsor's representative) or delegate within 24 hours of the Investigator being aware of the suspected SAE. The DSMB will be notified of SAEs that are deemed possibly, probably or definitely related to study interventions; the chair of DSMB will be notified immediately (within 24 hours) of the CI/sponsor being aware of their occurrence. SAEs which are related to a respiratory event will also be reported promptly to the DSMB. SAE will not normally be reported immediately to the ethical committee(s) unless there is a clinically important increase in occurrence rate, an unexpected outcome, or a new event that is likely to affect safety of trial participants, at the discretion of the Chief Investigator and/or DSMB. In addition to the expedited reporting above, the Investigator shall include all SAE in the annual Development Safety Update Report (DSUR) report.

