#### 15 Statistics

#### 15.1 Sample size

The primary objective of this study is to determine the relative risk of medially attended wheezing in 28 days following LAIV vaccination compared with placebo. The null and alternate hypotheses are:

H0: Proportion of wheezing LAIV = Proportion of wheezing Placebo

H1: Proportion of wheezing LAIV ≠ Proportion of wheezing Placebo

Where the proportion of wheezing is calculated as the number of participants with respiratory wheezing diagnosed by a health practitioner requiring medical attention within 28 days following receiving LAIV or a placebo. We chose 28 days as this is the common interval to observe intermediate reactions following vaccination. The study was a cross-over design, i.e. participants randomised to LAIV or placebo at Day0 will receive placebo or LAIV at Day28, respectively. Although there is no data on the ideal washout period, it is biologically reasonable to assume that the impact of LAIV will last shorter than 28 days. The data from a previous publication comparing medically significant wheeze rates between LAIV and inactivated vaccine groups reported 44 vs 20 cases in the first 28 days following vaccination, and 11 vs 14 cases between 29-42 days post-vaccination, further supporting our assumption. Therefore, we will use both Day 0-28 and Day 28-56 periods in the primary analysis in the primary analysis.

The sample size calculation is based on the below assumptions:

- 1. The proportion of medially attended wheezing is 0.9% following placebo in 28 days following vaccination;
- 2. The relative risk of interest is 2;

- 3. Study power of 80%;
- 4. Type I error of 0.05 two-sided;

Based on the above sample size, the study will need to recruit 2800 effective participants. Given the study endpoint will be extracted based on electronic medical records, we expect the attrition rate will be low. The total sample size will be 3000.

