#### 16.2 Data Recording

uMed securely collects clinical, patient-reported, and study data in compliance with GCP and regulatory standards. Data is obtained from the following primary sources:

- EHR Data: Extracted from UK general practices (EMIS and TPP systems)
- ePRO/eDiary/eConsent Data: Captured directly from patients via digital surveys for informed consent, subjective outcomes and other patient reported data as required by the Protocol
- Other Study Data: Collected from sites through digital Case Report Forms (CRFs) for protocolspecific activities

All data is stored and managed within uMed's secure cloud infrastructure on Amazon Web Services (AWS) in the London region (UK). Patient-identifiable data remains within this controlled environment. Data management includes strict governance, access control, audit logging, and filtering for National Data Opt-Out and exclusion criteria. Source data files are retained in their original form for traceability and auditability. Data handling adheres to GDPR and relevant local regulations, with access restricted to authorized personnel.

All participant reported adverse event data will be entered onto electronic diary cards (e-diaries) for a maximum of 28 days following administration of the IMP. The eDiary provides a full audit trial of edits and will be reviewed at time-points as indicated in the schedule of events. Any adverse event continuing beyond the period of the diary will be copied into the eCRF as required for safety review.

The participants will be identified by a unique trial specific number and code in any database. The name and any other identifying detail will NOT be included in any trial data electronic file, with the exception of the electronic diaries, for which consent will be obtained to store the participant email

address for quality control purposes. Only site research staff, sponsor staff, monitors (as delegated by sponsor) and University of Oxford data managers have access to view the email address.

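### Diary requests stop at day 14 of a 28-day outcome window, so non-admitted wheeze seen outside the child's own GP practice in days 15-28 rests on later recall, and up to 7 days may not be asked about at all

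*Protocol*

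**What the plan says.** Section 9 sets the primary outcome over "Day 0 to 28 following vaccination", and section 15.1 uses both 28-day periods. Section 9.1 takes wheeze mainly from GP records. Attendances elsewhere "will be determined using electronic diaries and solicited at follow up visits".

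Section 12.5.2 says parents "will receive a digital diary request at 7 and 14 days after each inperson study visit during the trial". Each request asks "whether their child has attended a healthcare provider since their last visit or diary entry", so the last one in each period looks back from day 14.

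Section 16.2 says participant-reported adverse event data "will be entered onto electronic diary cards (e-diaries) for a maximum of 28 days following administration of the IMP".

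The fallback contacts are visit 2 at D28 (-3/+7) and the digital questionnaire at D56 (+7), where medical attendances are solicited (sections 12.5.4 and 14.6.1, Appendix A). Hospital admissions also have a 24-hour telephone number and e-mail address (sections 12.5.2 and 14.7).

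**The concern.** The diary is a named source for part of the primary outcome, yet it is requested only in the first half of each window. For a child seen with wheeze in A&E or at another practice and sent home in days 15-28, the protocol names no study reporting route before the next scheduled contact. The admissions line is not meant for such a child, and section 14.7.1 says A&E attendances are not routinely SAEs.

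At stake is the completeness of a rare outcome. Events missed in the second half reduce the count on which the comparison rests. The further questions in 12.5.2 are described as covering where the contact took place and what it was for. A date is not mentioned, although one is needed to place an event inside a 28-day window and on the time-to-wheeze curve of section 15.2.

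**Working it through.** **1. Time from the last diary request to the next solicitation**

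Inputs: requests at days 7 and 14 after each in-person visit (12.5.2); visit 2 between D25 and D35, and questionnaire between D56 and D63 (Appendix A).

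| | Last request | Next solicitation | Gap |
|---|---|---|---|
| Period 1, nominal | D14 | D28 | 14 days |
| Period 1, longest | D14 | D35 | 35 - 14 = 21 days |
| Period 2, nominal | 28 + 14 = D42 | D56 | 14 days |
| Period 2, longest | 25 + 14 = D39 | D63 | 63 - 39 = 24 days |

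The 24 days needs the earliest visit 2 together with the latest questionnaire.

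**2. The end of the second window**

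With visit 2 on D35, the second window ends on 35 + 28 = D63. The last diary request is on 35 + 14 = D49. A questionnaire completed on D56 is within its allowed dates and cannot cover D57-D63, so 63 - 56 = 7 days have neither a diary request nor a question. With visit 2 on D28 the window ends on D56, and this hole closes.

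**3. The plan's own sample size**

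Inputs (15.1): 0.9% after placebo, relative risk 2 (so 1.8%), two-sided 0.05, 80% power. With p = (0.009 + 0.018)/2 = 0.0135:

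n = [1.960 √(2p(1-p)) + 0.842 √(0.009 × 0.991 + 0.018 × 0.982)]² / 0.009² ≈ 2580 per condition

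With the continuity correction this becomes 2798, which matches the stated 2800. Each child supplies both conditions, so this is 2800 children. Without the correction, power at 2800 is 83.1%.

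**4. What missed events would cost**

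The protocol does not give the share of wheeze seen outside the own practice. Assumptions: this share is 20-40%; recall without a diary misses 10-40% of such events in days 15-28; events are spread evenly over the window; the loss is equal after both products.

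- Loss among second-half events: 0.2 × 0.1 = 2% to 0.4 × 0.4 = 16%.
- Loss among all events: half of that, 1% to 8%.
- Expected events under the design assumptions: 2800 × (0.009 + 0.018) = 75.6, of which 25.2 follow placebo. A loss of 1-8% is about 1 to 6 events.

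Power is taken at 2800 per condition, with both proportions multiplied by (1 - loss), by the uncorrected formula:

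| Loss of all events | Power |
|---|---|
| 0% | 83.1% |
| 1% | 82.7% |
| 5% | 81.2% |
| 8% | 79.9% |
| 10% | 79.0% |

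The relative risk is unchanged by an equal loss: 0.018(1 - loss) / 0.009(1 - loss) = 2.

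**The case against.** The second half of each window is not left empty by design. Section 9.1 names two sources for attendances elsewhere, and follow-up solicitation is the second. Visit 2 is in person, non-responders to the final questionnaire are chased by the uMed nurse and then the local team (12.5), and concomitant medications are collected at D28 and D56, which is a further prompt about bronchodilators. The main source, the GP record, covers all 28 days. At nominal timing a day-28 request largely duplicates an existing contact. This all stands, and it is why the expected loss is small. It does not shorten recall from day 14 to the next contact, nor close the 7-day hole after a late visit 2.

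Four stronger readings are tempting, and the protocol does not support them.

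- **Late admissions also rest on recall, so the hospitalisation pause rule runs blind.** Admissions have a telephone and e-mail route with no day limit. The diary route, "Participant reports hospital admission in eDiary (uMed will then notify trial site", is one of three. Only an admission that the parent does not report could stay unknown until the next contact.
- **Sections 12.5.2 and 16.2 contradict each other.** Section 16.2 sets a maximum, and requests at days 7 and 14 comply with it. The two are unaligned, not contradictory.
- **The relative risk is biased.** Section 12.5.2 gives the same schedule after both products, and parents are blinded. No differential loss is shown.
- **A dip after day 14 would falsely support the washout.** Section 15.1 argues that "it is biologically reasonable to assume that the impact of LAIV will last shorter than 28 days" from biology and an earlier trial's counts. Section 15.2 adds a carryover test, and the Kaplan-Meier curve is only for display. Equal under-capture would lower both curves, and 2-16% of about 38 second-half events is 1 to 6 events.

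More prompts could also nudge healthcare seeking, which 12.5.2 wants left undisturbed. The two added messages ask the same question as the existing two and go out alike after both products, so this weighs little, though it cannot be excluded.

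**Conclusion.** The point holds for a limited group of events: wheeze without admission, seen outside the child's own practice, in days 15-28 after a product. For these the protocol relies on recall over 14 days at nominal dates, and over 21 or 24 days at the edges of the visit windows. When visit 2 is late and the questionnaire is completed early, up to 7 days of the second window go unasked.

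The expected harm is a modest loss of events, not a distorted comparison. A loss of 1-8% would bring power from about 83% to between 80% and 83%, close to the planned 80% even at the upper end. These figures rest on assumed shares that the protocol does not give, on even timing of events, and on equal loss after both products. The change is worth making because it is cheap and bears on the completeness of the primary outcome. The trial's validity does not depend on it.

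**What to change.** In section 12.5.2, send the same automated request at days 7, 14, 21 and 28 after each in-person visit, counted from the actual visit date. The longest step between requests is then 7 days, and after a visit 2 on D35 the last request falls on D63, the end of that window. Keep the questions at visit 2 and in the final questionnaire as back-up. Record the date of each attendance, so that an event can be assigned to the right period when visit 2 precedes D28.

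In the same amendment, state the diary duration identically in 12.5.2 and 16.2, and reconcile Appendix A with them. As printed, Appendix A gives diary information and diary review at D0 and D28 for the early vaccine group but at D28 and D56 for the late vaccine group. Read literally, that covers only the LAIV period in each group, whereas 12.5.2 sends requests after both visits.

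The cost is two more automated messages per period, a short amendment and slightly more burden on parents.

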#### 12.5.3 Safety review

Due to the rapid recruitment and short study period, there are no planned safety reviews whilst the study is ongoing. Safety reviews can be conducted on an ad-hoc basis as requested by the DSMB.

## 12.5.4 Subsequent visits

Follow-up visits will take place as per the schedule of attendances described in Appendix A. Participants will be assessed for medical attendances, interim history and review of diary cards at these time points as detailed in the schedule of attendances.

## 12.6 Early Discontinuation/Withdrawal of Participants

In accordance with the principles of the current revision of the Declaration of Helsinki and any other applicable regulations, a participants' parents/legal guardian has the right to withdraw them from the study at any time and for any reason, and are not obliged to give their reasons for doing so. The Investigator may withdraw the participant at any time in the interests of the participants' health and well-being. In addition, the participant may withdraw/be withdrawn for any of the following reasons:

- Administrative decision by the Investigator
- Ineligibility (either arising during the study or retrospectively, having been overlooked at screening).
- Significant protocol deviation

- Participant non-compliance with study requirements
- An AE, which requires discontinuation of the study involvement or results in inability to continue to comply with study procedures

The reason for withdrawal will be recorded in the CRF. If withdrawal is due to an AE, appropriate follow-up visits or medical care will be arranged, with the agreement of the volunteer, until the AE has resolved, stabilised or a non-trial related causality has been assigned. The DSMB or DSMB chair may recommend withdrawal of participants.

In cases of subject withdrawal, long-term safety data collection may continue as appropriate if subjects have received one or more vaccine doses, unless they decline any further follow-up.

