## 10.1.4 Early Vaccine (EV)

Participants randomised to EV will receive the study intervention of 0.2ml Fluenz nasal spray (0.1ml per nostril) on day 0. At the follow up visit on day 28 they will receive 0.2ml of 0.9% saline placebo nasal spray (0.1ml per nostril). Their final follow up visit will be on 56 post randomisation.

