## 14 Safety Reporting

## 14.1 Safety reporting window

Safety reporting for the trial will commence once the first participant is consented; and will end after the last participant has attended their final study visit for MAAEs and SAEs.

For individual participants the reporting period begins when consent is confirmed, in person, at the V1 visit, and ends after their final study visit.

All adverse events (AEs) that result in a participants' withdrawal from the study will be followed up until a satisfactory resolution occurs, or until a non-study related causality is assigned (if consent is provided).

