#### 15.2 Description of statistical methods

The primary analysis population will be participants who are randomised and received LAIV or placebo at Day 0 and Day 28. The proportion of participants with a diagnosis of medically attended wheezing between Day 0 to Day 28 and between Day 28 and Day 56, along with the associated 95% confidence intervals will be presented. When calculating the proportion, the numerator will be the number of participants randomised and received LAIV or placebo at the start of each period. The analysis will be conducted according to the vaccine received. The difference in proportions between the two arms will be analysed using Pearson's chi-squared test after combining the data from both periods. The corresponding 95% CI will be derived using a standard method. The risk of wheezing following LAIV will be estimated by a mixed-effects model with the study vaccine received at the start of each period, study period (months) and sequence as fixed effects and participant ID as a random effect to account for within-subject variability. The Kaplan-Meier curve will be used to visualise the time to medically attend wheeze. Participants who withdrew from the study will be censored in the analysis at the time of withdrawal. Non-diagnosed participants will be censored in the analysis at 28 days following vaccination in both periods.

Carryover effects were assessed by testing for the interaction between vaccine and sequence, and if significant, the comparison between the two groups will be done for the two periods separately. We will also test the interaction between the study period (by months) and the vaccine to understand if any increased risk observed following LAIV is affected by the background wheezing risk.

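### Post-withdrawal data collection in 12.6 is tied to an ambiguous vaccine-dose condition, and 15.2 can lose GP-record outcomes of children who stop early

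*Protocol*

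**What the plan says.** **Withdrawal (12.6).** Withdrawal is from the study, by the parent or by the investigator. The listed reasons include administrative decision, ineligibility, protocol deviation, non-compliance and an adverse event. Afterwards, "long-term safety data collection may continue as appropriate if subjects have received one or more vaccine doses", "unless they decline any further follow-up".

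**Products (10.1.4, 10.1.5).** On day 0, "Participants randomised to EV will receive the study intervention of 0.2ml Fluenz nasal spray". The late-vaccine arm receives saline on day 0 and LAIV only at day 28.

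**Reporting window (14.1).** "For individual participants the reporting period begins when consent is confirmed, in person, at the V1 visit, and ends after their final study visit". The section does not say what the final visit is for a child who has been withdrawn.

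**Analysis (15.2).** Three statements bear on early leavers:
- "The primary analysis population will be participants who are randomised and received LAIV or placebo at Day 0 and Day 28".
- For the period proportions, "the numerator will be the number of participants randomised and received LAIV or placebo at the start of each period". This count can only work as a denominator.
- After the Kaplan-Meier sentence: "Participants who withdrew from the study will be censored in the analysis at the time of withdrawal".

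**Outcome source (9.1, 15.1).** Wheeze is taken mainly from routine GP records, and 15.1 relies on this: "Given the study endpoint will be extracted based on electronic medical records, we expect the attrition rate will be low".

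**The concern.** Between Day 0 and Day 28 every dosed early-vaccine child has had LAIV, and every dosed late-vaccine child has had saline only. If vaccine dose means LAIV, the condition in 12.6 is met in one arm and not in the other, in the period that is free of carryover. Collection is discretionary, and delivery staff know the allocation (12.4, 13.1.3). A neutral rule would leave no room for arm-dependent follow-up.

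The second issue is separate. The outcome needs no visit and no diary from a child who stops early, because it sits in the GP record. Yet 15.2 can be read to discard it, either by censoring at withdrawal or by requiring both doses. That sits badly with 15.1, where the same records are the reason to expect low attrition.

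At stake are completeness of the wheeze outcome, even-handed collection of serious and medically attended adverse events (secondary outcomes throughout the study, section 9), and the hospitalisation comparison between arms in the holding rule (14.12).

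**Working it through.** **1. The plan's own figures.** Inputs from 15.1: placebo risk 0.9%, RR 2 (so LAIV 1.8%), 80% power, two-sided 0.05.
- Pooled two-proportion formula: n = 2,580 per condition.
- With continuity correction: (n/4) × [1 + √(1 + 4/(n × 0.009))]² = 645 × (1 + 1.0827)² ≈ 2,798.
- Each child supplies one LAIV and one placebo period, so this reproduces the stated 2,800.
- Implied attrition: 200/3,000 = 6.7%. Section 15.1 gives no percentage itself.

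**2. What each reading of 15.2 does to a child who leaves before Day 28.**

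| Reading | Wheeze estimate | What remains wrong |
|---|---|---|
| Both-doses population governs | Child is outside the analysis in either arm | First-period outcomes lost, including any recorded before withdrawal |
| Censoring governs the whole analysis | Later data unused in either arm | Retrievable outcomes after withdrawal discarded |
| All dosed at start of period are counted; censoring is for Kaplan-Meier only | Child stays in the denominator | If 12.6 is read literally, later events can be found only in early-vaccine children |

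Unequal follow-up reaches the wheeze estimate only in the third row. In the first two rows it can still affect the adverse-event and hospitalisation comparisons.

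**3. Size in the third row.** Assumptions: 1,500 per arm; true RR 1; placebo risk 0.9%; a fraction w of children leaves in period 1, evenly over the 28 days; early-vaccine leavers are fully observed; placebo-first leavers are lost at withdrawal and count as non-events if nothing was recorded. Leavers have k times the risk of stayers.

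Share of placebo events in leavers = wk/(1 − w + wk). Half is lost with even timing. Observed RR = 1/(1 − share lost).

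| w | k | Share lost | Period-1 RR |
|---|---|---|---|
| 0.067 | 1 | 0.067/2 = 3.35% | 1/0.9665 = 1.035 |
| 0.067 | 3 | (0.201/1.134)/2 = 8.86% | 1/0.9114 = 1.097 |
| 0.033 | 1 | 0.033/2 = 1.65% | 1.017 |
| 0.033 | 3 | (0.099/1.066)/2 = 4.64% | 1.049 |

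In events: 1,500 × 0.009 = 13.5 expected placebo events in period 1. The loss is 13.5 × 0.0335 = 0.45 events at k = 1 and 13.5 × 0.0886 = 1.2 events at k = 3, both with w = 0.067.

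Pooled over both periods at w = 0.067 and k = 1, with leavers absent from period 2: (1 + 0.933)/(0.9665 + 0.933) = 1.018.

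If all 6.7% left immediately after dosing, at average risk, the figures would be 1.07 in period 1 and 1.04 pooled.

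**The case against.** A reader might infer that the protocol follows first-period leavers in one arm and not in the other, and so biases the primary comparison. The documents do not support that.

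- Section 12.6 is permissive: collection may continue as appropriate. It speaks of long-term safety data and does not set the rule for the 28-day record extraction in 9.1, which has no arm-dependent condition.
- The word vaccine is often used for both products. Section 12.4 equates which vaccine a child receives with arm allocation, and the model in 15.2 has a study vaccine in each period. Each child gets only one LAIV dose, so a condition of one or more doses fits better if saline counts.
- Censoring in both arms, or the both-doses population, keeps the asymmetry out of the wheeze estimate.
- The censoring sentence stands beside the Kaplan-Meier sentence and probably governs only that curve. Detail on withdrawn children may be in a statistical analysis plan that is not shown.
- Sections 12.6 and 14.1 provide follow-up of adverse events that lead to withdrawal, in both arms.
- Even on the literal reading, the base case is less than half an event, and the error would make LAIV look slightly worse.

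Most of this stands, and it limits the point to ambiguity with a small likely effect. Three things remain. Section 13.1.3 contrasts vaccine with placebo, and nothing says that saline counts for 12.6. Following the event that caused withdrawal does not capture new events, or events in children withdrawn for other reasons. And an analysis plan cannot recover data that the protocol did not provide for collecting.

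**Conclusion.** The wording of 12.6 is ambiguous and could be applied unequally by staff who know the allocation. Separately, 15.2 can lose first-period outcomes that GP records would supply. These are alternatives: the bias in the wheeze estimate must not be added to the loss from censoring or from the both-doses population.

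Where the asymmetry does reach the estimate, a null RR would read about 1.03 in period 1 and about 1.02 pooled, against an RR of interest of 2. About 1.10 in period 1 needs leavers at three times the risk, for which the protocol gives no evidence. Placing all 6.7% attrition in period 1 is a high-end assumption; half of it gives about 1.02 to 1.05. The effect on adverse-event and hospitalisation comparisons cannot be sized from the protocol. Severity is minor to moderate and confidence moderate. The point is worth acting on because each reading of 15.2 either loses retrievable outcomes or leaves follow-up open to depend on the arm.

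**What to change.** - **12.6:** replace the condition of one or more vaccine doses with *either study product (LAIV or placebo)*. State that record extraction continues in both arms to the end of the 28-day window of the last product received, unless the parent declines. The opt-out is already there and can stay.
- **15.2:** include every child dosed at the start of a period in that period's proportion, and reconcile this with the both-doses population. Count events found in records after withdrawal. Censor only at the date on which the parent refuses further use of records.
- **14.1:** align the end of the reporting period with this for children who are withdrawn.

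The cost is protocol wording and one line in the information sheet. A few early leavers stay on the extraction list. No visits are added and the sample size does not change.
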